15.1. ADVERSE EVENTS

Adverse Events (AEs) will be coded using MedDRA central coding dictionary, Version 19.1 or higher. SOC's will be sorted by internationally agreed European Medicines Agency (EMA) SOC order (refer to [APPENDIX 4](#)), PTs will be sorted by decreasing frequencies (within system organ class).

In case of worsening in severity, a new entry is created with start date equal to start of worsening.

TEAEs are defined as AEs that started or worsened in severity on or after the first and single dose of trial medication up to 10 weeks (70 days) post dose.

See [APPENDIX 2](#) for handling of partial dates for AEs. In case it is not possible to define an AE as treatment emergent or not, the AE will be classified by the worst case; i.e. treatment emergent.

An overall summary of number of subjects within each of the categories described in the sub-section below, will be provided as specified in the templates.

Listings will include TEAEs and Non-TEAEs.

15.1.1. ALL TEAEs

Incidence of TEAEs will be presented by SOC and PT within each SOC and also broken down further by maximum severity and relationship to trial medication.

15.1.1.1. Intensity

Intensity is classed as mild/ moderate/ severe (increasing severity). TEAEs starting after the first dose of trial medication with a missing intensity will be classified as severe. If a subject reports a TEAE more than once within that SOC/ PT, the AE with the worst case intensity will be used in the corresponding intensity summaries.

15.1.1.2. Relationship to Trial Medication

A related TEAE is defined as a TEAE with a relationship to trial medication ticked "yes" according to the investigator. TEAEs with a missing relationship to study medication will be regarded as related to trial medication. If a subject reports the same AE more than once within that SOC/ PT, the AE with the worst case relationship (TEAE with a relationship to trial medication ticked "yes") to trial medication will be used in the corresponding relationship summaries.

15.1.2. SERIOUS ADVERSE EVENTS

Serious adverse events (SAEs) are those events recorded as "Serious" on the Adverse Events page of the eCRF. A summary of serious TEAEs by SOC and PT will be prepared. All SAEs as recorded in the

Document: \\ieedc-nas01a\BIOSdata\Boehringer_Ingelheim\BI_695501\EYA00232\Biostatistics\Documentation\SAP\BI_1297_13_SAP_09JAN2017_v1.0

Author: ██████████ Version Number: 1.0
Version Date: 09JAN2017

Template No: CS_TP_BS016 Revision 4 Reference: CS_WI_BS005
Effective Date: 01Apr2016

[REDACTED]
Statistical Analysis Plan

eCRF will be listed.

15.1.3. ADVERSE EVENTS LEADING TO DEATH

TEAEs leading to Death are those events which are recorded as “Results in death” on the Adverse Events page of the eCRF. A summary of subjects with TEAEs leading to death will be presented in overview summary. All AEs leading to Death as recorded in the eCRF will be listed.

15.1.4. ADVERSE EVENTS OF SPECIAL INTEREST (AESI)

An overall summary of the number of subjects and percentages within each of the categories described in the sub-sections below will be provided.

The risk difference between both treatment groups will be displayed together with its 95% confidence interval (CI).

The SAS code below will be used to produce exact unconditional CI for risk difference:

```
PROC FREQ data= Data;  
  TABLES trt*aesi_overall;  
  EXACT riskdiff(method=score);  
  WEIGHT count;  
RUN;
```

In addition, risk ratio will be displayed together with associated 95% exact confidence interval.

Risk ratio will be defined as: $(a/(a+b))/(c/(c+d))$.

Where **a** is the number of subjects with AESI within treatment group, **a+b** is the total number of subjects in treatment group, **c** is the number of subjects with AESI within treatment, **c+d** is the total number of subjects in treatment group.

PROC FREQ with option RELRISK will be used for programming purpose.

```
PROC FREQ data=data_AESI;  
  TABLES trt*aesi_overall;  
  EXACT relrisk(method=score);  
  WEIGHT count;  
RUN;
```

15.1.4.1. Reported by Investigator

AESI reported by investigators are those events recorded as “Adverse Event of Special Interest” equal to “Yes” on the Adverse Events page of the eCRF.

Number of subjects, percentages and number of events of Treatment Emergent AESI reported by investigators by SOC and PT table will be prepared.

| | | | |
|-----------------|---|-----------------|-------------|
| Document: | \\ieedc-nas01a\BIOSdata\Boehringer_Ingelheim\BI_695501\EYA00232\Biostatistics\Documentation\SAP\BI_1297_13_SAP_09JAN2017_v1.0 | Version Number: | 1.0 |
| Author: | [REDACTED] | Version Date: | 09JAN2017 |
| Template No: | CS_TP_BS016 Revision 4 | Reference: | CS_WI_BS005 |
| Effective Date: | 01Apr2016 | | |

████████████████████
Statistical Analysis Plan

15.1.4.2. Serious Infections

Infections are those events with a SOC equal to “Infections and infestations”.

Serious infections are:

- AEs which are both infections and SAEs as reported on the Adverse Events page of the eCRF.
- AEs which are both infections and identified by medical advisor as requiring class IV (intravenous) antibiotics.

Serious infections events of special interest are those events both identified as serious infections adverse events and recorded as “Adverse Event of Special Interest” equal to “Yes” on the Adverse Events page of the eCRF.

Number of subjects, percentages and number of events of Treatment Emergent Infections by SOC and PT tables will be prepared.

Number of subjects, percentages and number of events of Treatment Emergent Serious Infections by SOC and PT tables overall will be prepared.

Serious Infections will be listed. The listing will include the “Adverse Event of Special Interest” equal to “Yes” and the “Is the AE an infection?” equal to “Yes” information from the Adverse Events page of the eCRF as flags.

15.1.4.3. Hypersensitivity Reactions

Hypersensitivity reactions adverse events are those events recorded as MedDRA code in the pre-defined Standardized MedDRA Queries (SMQ) “Hypersensitivity” (narrow).

Hypersensitivity reactions adverse events of special interest are those events both identified as Hypersensitivity reactions adverse events and recorded as “Adverse Event of Special Interest” equal to “Yes” on the Adverse Events page of the eCRF.

Number of subjects, percentages and number of events of Treatment Emergent Hypersensitivity reactions by SOC and PT tables will be prepared.

Hypersensitivity reactions will be listed. The listing will include the “Adverse Event of Special Interest” equal to “Yes” information from the Adverse Events page of the eCRF as a flag.

15.1.4.4. Drug Induced Liver Injury (DILI)

Drug Induced Liver Injury (DILI) are those events identified by medical advisor on the subset of AEs for subjects presenting laboratory potential DILI findings (refer to [section 15.3.2](#)).

DILI events of special interest are those events both identified as DILI adverse events and recorded as “Adverse Event of Special Interest” equal to “Yes” on the Adverse Events page of the eCRF.

Document: \\ieedc-nas01a\BIOSdata\Boehringer_Ingelheim\BI_695501\EYA00232\Biostatistics\Documentation\SAP\BI_1297_13_SAP_09JAN2017_v1.0

Author: ██████████ Version Number: 1.0
Version Date: 09JAN2017

Template No: CS_TP_BS016 Revision 4 Reference: CS_WI_BS005
Effective Date: 01Apr2016

Statistical Analysis Plan

Number of subjects, percentages and number of events of Treatment Emergent DILI by SOC and PT tables will be prepared.

DILI will be listed. The listing will include the “Adverse Event of Special Interest” equal to “Yes” information from the Adverse Events page of the eCRF as a flag.

15.1.4.5. Injection-site Reactions

Injection-site reactions are those events recorded within the following subsearches of the BlcMQ “Administration site reactions” (narrow):

- Administration site reactions NEC (subsearch 1)
- Application and instillation site reactions (subsearch 2)
- Infusion site reactions (subsearch 4)
- Injection site reactions (subsearch 5)

Number of subjects, percentages and number of events of Treatment Emergent Injection-site reactions by SOC and PT tables will be prepared.

Injection-site reactions will be listed.

15.1.4.6. Anaphylactic Reactions

Anaphylactic reactions are those events recorded as MedDRA code in the pre-defined SMQ = “Anaphylactic reactions” (narrow).

Anaphylactic reactions adverse events of special interest are those events both identified as Anaphylactic reactions and recorded as “Adverse Event of Special Interest” equal to “Yes” on the Adverse Events page of the eCRF.

Number of subjects, percentages and number of events of Treatment Emergent Anaphylactic reactions by SOC and PT tables will be prepared.

Anaphylactic reactions will be listed. The listing will include the “Adverse Event of Special Interest” equal to “Yes” information from the Adverse Events page of the eCRF as a flag.

15.1.5. NON-SERIOUS TREATMENT EMERGENT AEs

Non-serious TEAEs are those events for which the investigator ticked “No” to the item “Is this a serious adverse event?” on the Adverse Events page of the eCRF.

Frequency of subjects, number of events and incidence of subject with non-serious TEAEs will be presented by SOC and PT, if preferred term total incidence >5%.

| | | | |
|-----------------|---|-----------------|-------------|
| Document: | \\weedc-nas01a\BIOSdata\Boehringer_Ingelheim\BI_695501\EYA00232\Biostatistics\Documentation\SAP\BI_1297_13_SAP_09JAN2017_v1.0 | Version Number: | 1.0 |
| Author: | | Version Date: | 09JAN2017 |
| Template No: | CS_TP_BS016 Revision 4 | Reference: | CS_WI_BS005 |
| Effective Date: | 01Apr2016 | | |

Statistical Analysis Plan

15.1.6. OTHER SIGNIFICANT AEs

Other significant AEs are not applicable in this single-dose trial as discontinuation, withdrawal or dose reduction cannot happen.

15.2. DEATHS

If any subjects die during the trial as recorded on the “End of trial visit” page of the eCRF, the information will be presented in a summary table and a data listing based on the RND set.

15.3. LABORATORY EVALUATIONS

Results from the central laboratory will be included in the reporting of this trial for Serum chemistry, Hematology, Coagulation, and Urinalysis. A list of laboratory assessments performed at screening, admission (Day -1), Day 8, Day 22 and Day 57 is included in [APPENDIX 3](#).

Presentations will use SI Units.

Quantitative laboratory measurements reported as “< X”, i.e. below the lower limit of quantification (BLQ), or “> X”, i.e. above the upper limit of quantification (ULQ), will be converted to X for the purpose of quantitative summaries, but will be presented as recorded, i.e. as “< X” or “> X” in the listings.

Qualitative laboratory urinalysis results measured by central laboratory will be classified to the categories “Positive” and “Negative” based on the central laboratory normal reference.

The handling of retests, unscheduled and end of trial measurements is described in [Section 6.3](#). However, laboratory values taken after the first and single dose of trial medication up to a period of 10 weeks after the last dose of the trial medication will be assigned to the treatment phase for evaluation. All available data (including IGRA results) will be listed.

In case the results of a laboratory parameter are reported in different units, depending on the site who performed the measurement, and no conversion factor between the two units is available, the laboratory parameter will be analyzed by site.

The following summaries will be provided for laboratory data:

- Actual and change from baseline by visit (for quantitative measurements)
- Shift from baseline category (Low / Normal / High) by visit (all parameters except urinalysis parameters)
- Shift from baseline category (Negative / Positive) by visit (for urinalysis parameters)
- Incidence of possible Hy's law subjects

Document: \\weedc-nas01a\BIOSdata\Boehringer_Ingelheim\BI_695501\EYA00232\Biostatistics\Documentation\SAP\BI_1297_13_SAP_09JAN2017_v1.0

Author: [REDACTED] Version Number: 1.0
Version Date: 09JAN2017

Template No: CS_TP_BS016 Revision 4 Reference: CS_WI_BS005
Effective Date: 01Apr2016

Statistical Analysis Plan

- Incidence of possible DILI
- The time course of ALT, AST and total bilirubin (TBL) for all possible Hy's law subjects, all parameters shown on a logarithm to base 10 scale of the multiple of the upper limit of normal (ULN) (Y axis) versus days since treatment start (X axis)
- Scatter plots for Evaluation of Potentially Drug-Induced Liver Injury:
 - log ALT on the X axis and log TBL on the Y axis, both shown on a logarithm to base 10 scale of the multiple of the ULN
 - log AST on the X axis and log TBL on the Y axis, both shown on a logarithm to base 10 scale of the multiple of the ULN

15.3.1. LABORATORY SPECIFIC DERIVATIONS

- Log ALT = logarithm to base 10 scale of the multiple of the ULN of ALT
- Log AST = logarithm to base 10 scale of the multiple of the ULN of AST
- Log TBL = logarithm to base 10 scale of the multiple of the ULN of TBL
- Potential Hy's law categories:
 - Category 1: ALT or AST $\geq 3 \times \text{ULN}$ and TBL $\geq 2 \times \text{ULN}$ within the same sample
 - Category 2: TBL $\geq 2 \times \text{ULN}$ within 30 days after transaminase peak (ALT or AST $\geq 3 \times \text{ULN}$)

Potential Hy's Law subjects are defined as subjects with laboratory data in at least one Potential Hy's law categories at any time point of the trial.

- Drug induced liver injury (DILI):
 - Category 1 : AST and/or ALT ≥ 3 times ULN and TBL ≥ 2 times ULN within the same sample
 - Category 2 : marked peak aminotransferase (ALT, and/or AST) elevations ≥ 10 fold ULN

15.3.2. LABORATORY REFERENCE RANGES AND MARKEDLY ABNORMAL CRITERIA

Quantitative laboratory measurements will be compared with the relevant laboratory reference ranges in SI units and categorized as:

- Low: Below the lower limit of the laboratory reference range.

Document: \\ieedc-nas01a\BIOSdata\Boehringer_Ingelheim\BI_695501\EYA00232\Biostatistics\Documentation\SAP\BI_1297_13_SAP_09JAN2017_v1.0

Author: [REDACTED] Version Number: 1.0
Version Date: 09JAN2017

Template No: CS_TP_BS016 Revision 4 Reference: CS_WI_BS005
Effective Date: 01Apr2016

Copyright © 2009, 2010, 2012, 2016 [REDACTED] Transnational Corp. All rights reserved.
The contents of this document are confidential and proprietary to [REDACTED] Transnational Corp. Unauthorized use, disclosure or reproduction is strictly prohibited.

Statistical Analysis Plan

- Normal: Within the laboratory reference range (upper and lower limit included).
- High: Above the upper limit of the laboratory reference range.

15.3.3. OTHER SAFETY LABORATORY EVALUATIONS

15.3.3.1. Pregnancy test

Descriptive table will present pregnancy results for females overall on SAF.

The pregnancy results will be listed as well on ENR.

15.4. ECG EVALUATIONS

Results from the central ECG (Electrocardiogram) will be summarized by visit to the categories as recorded in the eCRF page “12-Lead-ECG” (“normal”, “abnormal, not clinically significant” and “abnormal, clinically significant”).

In case of multiple assessments at the same date, the evaluation with the worst result is taken into account.

15.5. VITAL SIGNS

The following Vital Signs measurements will be reported for this trial:

- Systolic Blood Pressure (mmHg)
- Diastolic Blood Pressure (mmHg)
- Pulse Rate (bpm)
- Temperature (°C)
- Weight (kg)

The handling of retests, unscheduled and end of trial measurements is described in [Section 6.3](#).

The summary of actual and change from baseline by visit will be provided for vital sign data. In case of multiple measurement time points at one visit, the pre-administration data will be considered or the last available measurement at a specific visit (if pre-administration data is not applicable) will be used for summary tables.

Document: \\eedc-nas01a\BIOSdata\Boehringer_Ingelheim\BI_695501\EYA00232\Biostatistics\Documentation\SAP\BI_1297_13_SAP_09JAN2017_v1.0

Author: [REDACTED] Version Number: 1.0
Version Date: 09JAN2017

Template No: CS_TP_BS016 Revision 4 Reference: CS_WI_BS005
Effective Date: 01Apr2016

Copyright © 2009, 2010, 2012, 2016 [REDACTED] Transnational Corp. All rights reserved.
The contents of this document are confidential and proprietary to [REDACTED] Transnational Corp. Unauthorized use, disclosure or reproduction is strictly prohibited.

████████████████████
Statistical Analysis Plan

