3.2 DISCUSSION OF TRIAL DESIGN, INCLUDING THE CHOICE OF CONTROL GROUP(S)

This is a 14-week, open-label, randomized, single dose, parallel arm trial to investigate and compare the PK, safety, tolerability and immunogenicity of BI 695501 administered subcutaneously in the thigh via prefilled syringe or autoinjector.

Due to the long half-life of BI 695501, a parallel group design was selected, with administration of BI 695501 as a single dose only. Additionally, randomization minimizes selection bias between the treatment groups.

Blinding is not possible because the BI 695501 presentations are visually distinguishable. The open-label treatment is not expected to bias the PK results, since the trial endpoints are derived from measurement of plasma concentrations of the analyte provided by a bioanalytical laboratory which is blinded to treatment allocation.

It is not expected that the device itself, being a prefilled syringe or an autoinjector, has an influence on the bioavailability in terms of rate and extent of absorption especially considering the long half-life of the compound. The most likely important variable is the reliability of the injection with regards the depth of the injection and thus the tissue reached as well as the amount of drug being injected by the device. The injection characteristics are

more likely influenced by the amount of s.c. fat tissue. Body mass index and weight have a good correlation with s.c. fat tissue thus the inclusion of healthy subjects having a broad range of weight would give a better estimation of the reliability and performance of the devices.

The group size of up to 80 subjects per treatment group is considered adequate for an evaluation of the PK, safety, tolerability, and immunogenicity for the primary analysis report to support the primary objective of the study.

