6. INVESTIGATIONAL PLAN

6.1 VISIT SCHEDULE

Exact times of measurements outside the permitted time windows will be documented. The acceptable time windows for all visits are given in [Flow Chart](#).

- General medical examination: at screening (2 to 28 days prior to the first trial day);
- Trial measurements and assessments scheduled to occur 'before' trial medication administration on Day 1 are to be performed and completed within a 2 hour period prior to the trial drug administration.
- The acceptable deviation from the scheduled time for vital signs, ECG and laboratory tests PK, ADA, nAb sampling) will be:
 - ± 15 minutes for Day 1
 - ± 2 hours from Day 2 to Day 10;
 - ± 1 day from Day 15 to Day 57
 - The e.o.t. IGRA may be performed up to 72 hours prior to the other e.o.t. assessments.

If scheduled in the Flow Chart at the same time as a meal, vital signs, 12-lead ECG recordings and blood sampling have to be done first. Furthermore, if several measurements including venipuncture are scheduled for the same time, venipuncture should be the last of the measurements due to its inconvenience to the subject and possible influence on physiological parameters.

For planned individual plasma concentration sampling times refer to Flow Chart. While these nominal times should be adhered to as closely as possible, the actual sampling times will be recorded and used for determination of PK parameters.

If a subject misses an appointment, it will be rescheduled if possible. The relevance of measurements outside the permitted time windows will be assessed no later than at the Report Planning Meeting.

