3. TRIAL DESIGN

3.1. GENERAL DESCRIPTION

Trial 1297.13 is a 14-week, randomized, single-dose, open-label trial in healthy volunteers.

Each subject will receive one subcutaneous injection with either 40 mg BI 695501 autoinjector (AI) or 40 mg BI 695501 prefilled syringe (PFS) followed by an observation period of approximately 57 days and an additional safety follow-up period up to 70 days after the trial drug administration. Subjects who meet all the inclusion criteria and none of the exclusion criteria will be randomly assigned to one of the two groups with a 1:1 allocation ratio. Randomization will be stratified by site (2 levels and for logistical reasons only) and body weight category (low: ≤ 60.0 kg, medium: > 60.0 to < 90.0 kg, high: ≥ 90.0 kg).

It is planned to include 160 healthy male and female subjects (at least 30% of each gender will be included in the trial) with a broad range of weight for the primary analysis report describing the PK profiles of BI 695501 given in a PFS and an AI as well as the assessments of safety and immunogenicity. All efforts will be made to enroll subjects in all subgroups, in order to ensure a wide distribution of weight in the study.

This trial will have a screening period of up to 28 days. The subject will check in to the trial center on Day-1, will be randomized and dosed on Day 1, and will be resident until the Day 8 discharge procedures are complete. All subjects will remain in the clinic until Day 8 after dosing. The subject will then return to the clinic for 7 ambulatory visits on Days 10, 15, 22, 29, 36, 43 and 57 (End-of-Trial [EOT] visit).

Additionally, all adverse events (AEs), regardless of relatedness, will be collected until up to 10 weeks after the administration of trial medication. Adverse events not fully resolved at the safety follow-up (SFU) visit (Day 70 visit) will be followed until recovery or in case of persistency, sufficient characterization has been achieved and the investigator and medical monitor agree to not pursue them further.

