15. SAFETY OUTCOMES

All outputs for safety outcomes will be based on the SAF.

There will be no statistical comparisons between the treatment groups for safety data, unless otherwise specified with the relevant section.

The secondary safety endpoint is defined as the number (proportion) of subjects with drug-related treatment emergent adverse events (TEAEs) occurring from Day 1 through Day 70.

Safety and tolerability of the investigational products will be assessed based on:

- TEAEs (including clinically relevant findings from the physical examination and AESIs)
- Safety laboratory tests
- 12-lead ECG
- Vital signs (Blood pressure, pulse rate, temperature)

Document: \\ieedc-nas01a\BIOSdata\Boehringer_Ingelheim\BI_695501\EYA00232\Biostatistics\Documentation\SAP\BI_1297_13_SAP_09JAN2017_v1.0

Author: [REDACTED] Version Number: 1.0
Version Date: 09JAN2017

Template No: CS_TP_BS016 Revision 4 Reference: CS_WI_BS005
Effective Date: 01Apr2016

████████████████████
Statistical Analysis Plan

- Local tolerability

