15.7. OTHER SAFETY ASSESSMENTS

15.7.1. IMMUNOGENICITY EVALUATION

All outputs for Immunogenicity will be based on the SAF. There will be no inferential statistical comparisons between the treatment groups for immunogenicity data.

The following summary tables will be provided for immunogenicity data:

- Number and frequency of subjects with the following anti-drug antibody (ADA) / neutralizing anti-drug antibodies (nAbs) sampling results, by visit (baseline, Day 22, Day 57 and overall):
 - Negative
 - Positive
 - Total reportable (= sum of Negative and Positive)
 - Not Reportable (=no sample available or invalid sample)
 - Total (= sum of Total Reportable and Not Reportable)
- Descriptive statistics of ADA titers will be provided by visit (baseline, Day 22, Day 57 and overall), when available

The ADA and nAb results will be listed as well.

Following figures will be generated:

- Time course of ADA development (percent positive subjects) over time for all treatments
- Box plot (with whiskers) of titer within ADA positive subjects over time: at baseline, Day 22, and Day 57.
- Box plot (with whiskers) of titer within ADA positive subjects at each ADA timepoint (multiple graphs; baseline, Day 22, and Day 57)
- Time course of nAb development (percent positive subjects) over time (by planned visit day) for all treatments

Document: \\weedc-nas01a\BIOSdata\Boehringer_Ingelheim\BI_695501\EYA00232\Biostatistics\Documentation\SAP\BI_1297_13_SAP_09JAN2017_v1.0

Author: ██████████ Version Number: 1.0
Version Date: 09JAN2017

Template No: CS_TP_BS016 Revision 4 Reference: CS_WI_BS005
Effective Date: 01Apr2016

Copyright © 2009, 2010, 2012, 2016 ██████████ Transnational Corp. All rights reserved.
The contents of this document are confidential and proprietary to ██████████ Transnational Corp. Unauthorized use, disclosure or reproduction is strictly prohibited.

[REDACTED]
Statistical Analysis Plan

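### SAP 15.5 keeps one vital-sign value per visit, so at least one scheduled post-injection reading on the dosing day, normally the 1 h reading, is left out of the by-treatment summary

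*SAP*

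**What the plan says.** SAP 15.5 promises actual values and changes from baseline by visit for blood pressure, pulse rate, temperature and weight. For a visit with several readings it gives a selection rule: "In case of multiple measurement time points at one visit, the pre-administration data will be considered or the last available measurement". The second option is conditional: "if pre-administration data is not applicable) will be used for summary tables". No other part of the SAP text adds a vital-sign summary by time point.

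SAP 15 lists "Vital signs (Blood pressure, pulse rate, temperature" among the data on which safety and tolerability will be assessed. Protocol 3.2 describes the trial as one "to investigate and compare the PK, safety, tolerability and immunogenicity of BI 695501" given by the two devices. Protocol 7.3.4 asks for observed values and changes in blood pressure, pulse rate and temperature by treatment group and leaves the detail to the statistical analysis plan.

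Protocol 6.1 treats vital signs as timed measurements. Its list of time windows opens with "The acceptable deviation from the scheduled time for vital signs, ECG and laboratory tests" and allows 15 minutes either way on Day 1. SAP 6.2 defines baseline as the last non-missing value before dosing, and SAP 6.6 defines change as the value at the visit minus baseline.

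**The concern.** The trial gives a single injection and compares two ways of delivering it. The vital signs most directly tied to the injection are those taken in the hours after it. Protocol 5.7 says the scheduled measurements are there so that changes caused by dosing can be monitored. A rule that prefers the pre-dose value, or else the latest one, keeps the readings furthest from the injection and drops those closest to it.

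What is at stake is modest. The report would lack a by-device view of a small average shift soon after injection, too small in any one subject for the investigator to record as an adverse event. The documents give no evidence that such a shift is expected. The point is that the readings are planned and the table meant to show them does not.

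**Working it through.** The plan states no figure on this point, so the check applies the SAP 15.5 rule to each plausible reading of the Day 1 schedule and of the word visit.

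**What the flow chart supports.** The vital-sign column is the second from the right, next to adverse events and concomitant medication. The extracted Day 1 rows hold 16 cells against 15 column headings, so the right-hand marks have shifted.
- With a shift of one column, the 1 h and 4 h rows carry vital signs plus adverse events, and the pre-dose and 30-minute rows carry adverse events only.
- With a shift of two columns, the 1 h and 4 h rows carry ECG plus vital signs, and the pre-dose and 30-minute marks become vital signs. So do the 12 h, 24 h and 48 h marks. The arrow in the 60 h row, set beside the 48 h mark, fits this alignment if the arrow belongs to the adverse-event column.

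The 1 h and 4 h rows carry a vital-sign mark under both alignments. Whether the pre-dose row and the other rows do is unresolved.

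**What visit means.** The SAP mostly uses it for a study day. It speaks of "7 ambulatory visits on Days 10, 15, 22, 29, 36, 43 and 57", summarises antibody results "by visit (baseline, Day 22, Day 57 and overall", and lists laboratory tests as "performed at screening, admission (Day -1), Day 8, Day 22 and Day 57". A flow-chart footnote also calls Days -1 to 8 inpatient visits. However, the flow chart numbers the whole inpatient stay as Visit 2, and none of these places names Day 1 as a visit of its own.

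**Applying the rule.**
1. *Visit is the study day, with no Day 1 pre-dose reading.* The fallback applies and the last Day 1 reading is kept. The 1 h reading drops out when a later one exists. If every later one is missing, 1 h is kept.
2. *Visit is the study day, with a Day 1 pre-dose reading, scheduled or unscheduled.* The pre-dose value is kept, and every Day 1 post-injection reading drops out whether or not others are missing.
3. *Visit is numbered Visit 2.* The pre-administration value (Day -1, or Day 1 pre-dose if taken) is kept. Every Day 1 post-injection reading drops out, and so does the Day 8 reading.

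**Change from baseline in cases 2 and 3.** By SAP 6.6, change = value at visit − baseline. By SAP 6.2, baseline is the last value before dosing. When the value kept for the visit is that same value, change = baseline − baseline = 0 for every subject in both arms. The exception is a subject with more than one pre-administration value where the one kept is not the last.

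**Parameters affected.** Systolic pressure, diastolic pressure, pulse rate and temperature. Weight is not affected, because Protocol 5.3.1 places it at screening and end of treatment.

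**A neighbouring rule.** SAP 15.4 keeps the worst ECG evaluation when there are several on one date. SAP 15.5 keeps the pre-dose or the latest value, and no reason is given for the difference.

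**The case against.** The strongest objection is that the schedule comes from a broken table. A reader might infer that Day 1 has vital signs at exactly 1 h and 4 h, that the rule therefore omits half of the post-dose readings, and that 1 h is lost only while 4 h is present. The documents do not support that precision. The columns fit two alignments, and the rule's mention of pre-administration data may mean that a Day 1 pre-dose reading is taken. This part of the objection stands, so no counts are given and no time points are fixed in the proposed text.

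A second objection is that the output templates, which SAP 8 says set the format and content of the tables, are not among the documents and may already show time points. That is possible. If so, the text of SAP 15.5 disagrees with them and still needs a correction.

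A third is that little is lost. SAP 6.3 keeps scheduled and unscheduled readings in the listings. Protocol 5.3.7.2 requires clinically relevant vital-sign changes to be recorded as adverse events. SAP 15.1.4 tabulates hypersensitivity and anaphylactic reactions separately. Both arms receive the same 40 mg product, and Protocol 2.3 reports no clinically relevant vital-sign findings in trial 1297.8. All of this stands and sets the priority. It does not make the rule suitable for showing post-injection values.

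**Conclusion.** The point holds as a low-priority improvement. Under every reading examined, SAP 15.5 leaves at least one scheduled Day 1 post-injection reading out of the by-treatment summary for four parameters when the planned readings are taken. The 1 h reading is left out whenever a later or a pre-dose value exists. If a pre-administration value is kept, the summary shows no Day 1 post-dose value, and its change from baseline is normally zero by construction.

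This rests on the 1 h and 4 h rows of the flow chart both carrying vital signs, which both alignments give, and on the templates not overriding the SAP text.

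Two stronger conclusions should not be drawn. This is not a conflict with the protocol, because Protocol 7.3.4 leaves the presentation to the analysis plan. It also does not mean that a safety signal would go unseen, because listings, adverse-event recording and the special-interest tables remain. No primary or secondary endpoint is affected.

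**What to change.** In SAP 15.5, for blood pressure, pulse rate and temperature, replace the one-value-per-visit rule with text such as: *Actual values and change from baseline (SAP 6.2) will be summarised by treatment at each planned post-dose time point in the protocol flow chart; pre-administration values are used only as baseline.* Take the time points from the flow chart itself rather than typing a list into the SAP. Leave weight by visit. If the templates already show time points, align the SAP text with them.

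The cost is a wording change and some extra rows in a descriptive table. It needs no new data and adds no tests, and it removes the need to settle what visit means for these parameters.
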